#### 5.3.9 Primary Functional Patency

As defined for primary patency with duration of evaluation adjusted to start from first successful HD AV access use for HD using 2-needle cannulation. See Section 5.3.7 for defining the failure for primary functional patency.

The binary definition for primary functional patency is shown as below:

- If any failure event(s) as described in Section 5.3.7 occurs on or before the end of a specific visit window (e.g., 180+30 = Day 210 for 6-month visit), the participant is considered as having an event (loss of primary functional patency).
- If the participant was as transferred to PD, or had a kidney transplant, or had access discontinuation, or discontinued before the end of a specific visit window (e.g., 180+30 = Day 210 for 6-month visit) without the event, the participant is considered not evaluable and will not be included in the analysis.
- Otherwise, if the participant did not have any failure event(s) and has passed the specific visit window by the cutoff date of database lock, the participant is considered as not having an event.

This endpoint will be evaluated on the AT population and on the AT population with attainment of first successful HD AV access use for HD using 2-needle cannulation (on the EndoAVF Dialysis page, Date endoAVF Successfully Used with 2 Needles for Hemodialysis is not NULL). The proportion of primary functional patency (100% - event rate) and the 95% two-sided CI will be provided using the Clopper-Pearson method. For the 6-month reporting, the primary functional patency rate up to 6-months (up to Day 210) will be presented. For the final reporting, the primary functional patency rate up to 24-months (up to Day 760) will be presented.

#### 5.3.10 CVC Exposure /Use

#### 5.3.10.1 Duration of CVC Use Since Index Procedure

For participants with a CVC "in place" at the index procedure, data will be collected after HD AV access creation to investigate the duration of CVC use. The duration of CVC use since index procedure will be evaluated at 30-days, 6-weeks, 3-, 6-, 12-, 18-, and 24-months post creation for the participants with a CVC in place (or placed) at the index procedure. This analysis will only be performed for the participants with a CVC in place (or placed) at the index procedure from the AT population.

For each participant, the "true" Date of Removal of the first CVC placement will be identified, i.e., when a participant has a chain of CVC placements where the Date of Placement of an exchanged CVC is within one day of the Date of Removal of the previous CVC, it is considered as a CVC replacement, and the last Date of Removal of the chain of CVC placements will be used for the analysis.

Kaplan-Meier (KM) analysis will be used to estimate the time to CVC removal since the index procedure.

- If CVC removal occurs, the participant is considered as having the event, and the corresponding date of removal will be used in the analysis.
- If the participant was transferred to PD, or had a kidney transplant, or discontinued before the end of a specific visit window (e.g. Day 210 for 6 months post creation) without CVC removal, the participant is considered as censored at the earliest date among these events (i.e. PD start date, kidney transplant date, last date of available study data including the unscheduled visit date).
- Otherwise, if the participant is still in the investigation without having the CVC removed and have passed a specific visit by the cutoff date of database lock, the participant will be censored at the end of a specific visit window (e.g., 180+30 = Day 210 for the 6-month reporting, 730+30 = 760 for the 24-month reporting) for this analysis.

The number of participants with events, number of participants censored, time to event (days), and proportion of participants with events along with the 95% CI will be presented.

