• All Interventions After First Use (Facilitation, Maintenance and HD Continuity Interventions)

As defined for the exploratory endpoint directly above with duration of evaluation adjusted to start from first successful HD AV access use.

• Primary Patency

The time from HD AV access creation to the first one of the following events: access thrombosis; any facilitation or maintenance intervention intended to support maturation or cannulation, as well as those to maintain, or re-establish functionality*; access abandonment (as defined in Section 4.4); the access reaches an access censoring event as specified a priori in this CIP; or analysis timepoint / clinical investigation end. *Excludes adjunctive and second stage procedures.

• Cumulative Patency

The time from HD AV access creation to access abandonment, when the access reaches an access censoring event as specified a priori in this CIP, or analysis timepoint / clinical investigation end.¹⁸

• Primary Functional Patency

The time from first successful HD AV access use for HD using 2-needle cannulation to the first one of the following events: access thrombosis; any facilitation or maintenance intervention intended to support maturation or cannulation as well as those to maintain or re-establish functionality*; access abandonment (as defined in Section 4.4); the access reaches an access censoring event as specified a priori in this CIP; or analysis timepoint / clinical investigation end. *Excludes second stage procedures.

• Cumulative Functional Patency

As defined for the secondary endpoint (see Section 4.2.2.2) evaluated through additional time intervals.

• CVC Exposure / Use

Data will be collected regarding CVC exposure and use.

- For participants with a CVC in place at the index procedure, data will be collected after HD AV access creation to investigate the duration of CVC use.
- For all participants, data will be collected to determine frequency of CVC placements, time to CVC removal, total days of CVC exposure, and total days of CVC use.

• DUS Juxta/Peri-Anastomotic Area and Perforator Vein Patency

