4.4 Applicable Endpoint Definitions

Access Abandonment (permanent abandonment) is defined as the point at which the access can no longer be used for one or two needle prescribed HD as it may be unable to provide adequate flows and / or is deemed unsafe for the participant, and the associated problem cannot be corrected by any further intervention, including medical, surgical, or endovascular interventions or rest.^{8,19} Participants with an abandoned index AVF will continue with follow-up through 24-months and data will be collected on safety and interventions.

A HD AV access is not considered abandoned:

- If the participant discontinues use of the AV access due to kidney transplant, initiation of PD, or participant preference.
- During the maturation period or while waiting for a second stage procedure unless the principal investigator (PI) determines the participant requires and they then receive an alternative HD vascular access.

- During planned interventions, including transposition.
- If all reasonable efforts have not been attempted (and documented) to improve the condition of the access for it to be used.

A discontinuation of use of the clinical investigation AVF for any reason that does not meet this definition of access abandonment will be considered a temporary interruption.

Access Circuit Censoring Events include participant transfer to PD, kidney transplantation or the event of a participants premature discontinuation in the investigation due to withdrawn consent, withdrawal by PI, Lost to Follow-Up (LTF), or participant death (refer to Section 6.5 for definitions).

Adjunctive Procedure(s): Procedure(s) completed during the index procedure (prior to leaving the procedure room) as part of Standard-of-Care (SOC) procedures. These may include procedures to facilitate maturation and / or cannulation of the AVF, procedures to maintain use of the AVF, procedures to ensure HD continuity, as well as procedures to address AFs.

Second Stage Procedure(s): Facilitation Interventions (as defined below) intended to support the cannulation of arterialized vein segments that are determined to be needed a priori to or at the time of the index procedure (i.e. pre-planned facilitation interventions intended to support cannulation). Second stage procedures will not count against the intervention or patency endpoints and will require completion of the Second Stage Procedures eCRF.

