7.3 Sample Size Considerations

The sample size for the study of one-hundred and fifty (150) treated participants was established to assure adequate power for the primary safety and effectiveness endpoints as

well as to result in a sufficient sample size (when accounting for attrition) for assessment of the secondary and exploratory endpoints, specifically for those that only apply to subsets of the overall population (i.e. the incident population and wrist arterial procedure access population).

- 1) *Primary Safety Endpoint* The proportion of participants with freedom from device-or procedure-related SAEs through 30 days (ITT Population).
 - Assumptions:
 - The freedom from device- or procedure-related SAE rate for AVFs created using the WavelinQTM EndoAVF System is estimated at 92.6% through 30 days based on pre-market data;
 - The PG is set at 82.6% using a 10% non-inferiority margin;
 - The rate of attrition through 30 days is assumed to be 10%; and
 - o The Type 1 error is 0.05 (two-sided).
 - Sample Size:
 - A sample size of 150 treated participants [135 evaluable] will give over 92.5% power with a two-sided type I error of 0.05 as calculated using PASS 2019 (One Proportion Exact Test).
- 2) Primary Effectiveness Endpoint Interventions Post Creation to Facilitate AVF Use and / or Maintain AVF Use (Facilitation and / or Maintenance Interventions) through the Timepoint of the 6-Month Follow-Up of the Last Active Treated Participant (AT Population)
 - Assumptions:
 - The number of interventions post creation to facilitate AVF use and / or maintain AVF use after AVF creation using the WavelinQTM EndoAVF System is estimated at 3.0 / PY, a conservative assumption based on pre-market data;
 - The PG is set at 5 / PY to align with the targets and recommendations of the 2019 update of the KDOQI Clinical Practice Guideline for Vascular Access of < 2 interventions to facilitate and < 3 interventions to maintain AVF use;
 - The rate of attrition through 6-, 12-, and 24-months, including lost to followup, death, and other clinical investigation premature withdrawals is assumed to be 20%, 40%, and 60%, respectively; and
 - o The Type 1 error is 0.05 (two-sided).
 - Sample Size:
 - O A sample size of 150 treated participants, yielding more than 100 PY by the time the last active treated participant completes their 6-month follow-up, will give over 99% power with a two-sided type I error of 0.05 as calculated using PASS 2019 (One-Sample Poisson Rate Test).

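### Time to CVC removal: censoring participants who die with the catheter in place biases the Kaplan-Meier removal proportion upward

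*SAP*

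**What the plan says.** CIP 4.3 lists CVC exposure and use among the exploratory endpoints and says of the whole cohort that "data will be collected to determine frequency of CVC placements, time to CVC removal, total days of CVC exposure, and total days of CVC use". SAP 5.3.10.1 sets the method for participants with a catheter in place or placed at the index procedure:

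- Estimator: "Kaplan-Meier (KM) analysis will be used to estimate the time to CVC removal since the index procedure".
- Event: "If CVC removal occurs, the participant is considered as having the event, and the corresponding date of removal will be used in the analysis". A chain of exchanges counts as one catheter, dated at its last removal.
- Censoring: "If the participant was transferred to PD, or had a kidney transplant, or discontinued before the end of a specific visit window" and "without CVC removal, the participant is considered as censored at the earliest date among these events".
- Output: among other items, the "proportion of participants with events along with the 95% CI will be presented". With a Kaplan-Meier analysis this is naturally read as 1 minus the Kaplan-Meier estimate (1-KM), although the SAP does not write it that way.

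Evaluation times run from 30 days to 24 months. SAP 5.3.10.2 applies the same analysis to the whole As-Treated population.

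Death is not named in SAP 5.3.10.1. It enters through discontinuation: the censoring events in CIP 4.4 include "premature discontinuation in the investigation due to withdrawn consent, withdrawal by PI, Lost to Follow-Up (LTF), or participant death", and CIP 6.5 lists death among the reasons for discontinuing. Neither document mentions competing risks, cumulative incidence or a sensitivity analysis for this endpoint.

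**The concern.** Kaplan-Meier censoring assumes that a censored participant could still have the event later, at the same rate as those who remain. That can be reasonable for withdrawal, loss to follow-up or the data cut. It fails for death with the catheter in place, because removal can no longer happen. The estimator shares that participant's weight among those still at risk, so later removals count for more than they should. The removal proportion comes out too high and the time to removal looks shorter.

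Shorter catheter exposure is one of the potential benefits named in CIP 9.2, and the trial has a single arm, so no comparator carries the same bias and offsets it. What is at stake is how one exploratory figure reads, chiefly at the later time points, where deaths have accumulated.

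**Working it through.** **No stated figure.** The documents give no expected removal rate, number of participants with a catheter, or power for this endpoint, so there is nothing to reproduce. The direction can be shown exactly. The size can only be illustrated.

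**Direction.** Assumed example: 100 participants have a catheter, 20 die at day 60 with it in place, and 40 of the other 80 have it removed at day 90.

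- SAP rule: 1 − (1 − 40/80) = 50%.
- Actually removed: 40/100 = 40%.

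The 20 deaths are credited with 10 removals, half of one each. In general the excess is the sum, over deaths with the catheter in place at time u, of the share dying × [1 − S(24)/S(u)], where S is the Kaplan-Meier probability of still having the catheter. No term is negative. The sum is above zero as soon as any removal follows such a death, whatever rates are assumed.

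**Illustration 1.** Assumed: 1-KM of 60% at 6 months and 85% at 24 months, and a constant competing hazard with net probability p by 24 months.

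- Removal hazard, 0 to 6 months: λ1 = −ln(0.40)/0.5 = 1.833 per year.
- Removal hazard, 6 to 24 months: λ2 = −ln(0.15/0.40)/1.5 = 0.654 per year.
- Competing hazard: γ = −ln(1 − p)/2.
- Cumulative incidence at 24 months = λ1/(λ1+γ) × [1 − e^(−0.5(λ1+γ))] + e^(−0.5(λ1+γ)) × λ2/(λ2+γ) × [1 − e^(−1.5(λ2+γ))].

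For p = 20%, γ = 0.112. The first term is 0.586 and the second is 0.378 × 0.854 × 0.683 = 0.221, together 80.7%.

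| Net competing probability by 24 months | Competing event with catheter still in | 1-KM | Cumulative incidence | Excess |
|---|---|---|---|---|
| 10% | 3.6% | 85% | 82.9% | 2.1 points |
| 20% | 7.3% | 85% | 80.7% | 4.3 points |
| 30% | 11.2% | 85% | 78.3% | 6.7 points |

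In the 20% row each competing event is credited with 4.3/7.3 = 0.59 of a removal on average. For scale, the Greenwood standard error at 24 months with 60% censoring is 6.0 points for 60 participants and 4.9 for 90 (both numbers assumed). The excess is then about 0.4, 0.7 to 0.9, and 1.1 to 1.4 standard errors in the three rows.

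**Illustration 2, anchored on planned attrition.** CIP 7.3 gives attrition through 6, 12 and 24 months, "including lost to followup, death, and other clinical investigation premature withdrawals is assumed to be 20%, 40%, and 60%, respectively". The implied hazards are:

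- 0 to 6 months: −ln(0.8)/0.5 = 0.446 per year.
- 6 to 12 months: −ln(0.6/0.8)/0.5 = 0.575 per year.
- 12 to 24 months: −ln(0.4/0.6)/1 = 0.405 per year.

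Assume that a share s of this hazard is competing events and that the removal hazard is constant. With 1-KM of 50% at 6 months and s = 0.5:

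| Time | 1-KM | Cumulative incidence | Excess |
|---|---|---|---|
| 6 months | 50.0% | 47.6% | 2.4 points |
| 12 months | 75.0% | 68.6% | 6.4 points |
| 24 months | 93.8% | 82.1% | 11.7 points |

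Over 6-month values of 30% to 85% and s from 0.25 to 1, the excess is 0.8 to 6.3 points at 6 months, 2.6 to 11.9 at 12 months and 2.9 to 21.6 at 24 months.

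**The case against.** The strongest reply is that nothing depends on this figure. The endpoint is exploratory, has no hypothesis or performance goal, and under CIP 7.6 may not be reported at all. Numbers with events and numbers censored will appear beside the proportion, and discontinuations are tabulated by reason, though not by catheter status. CIP 9.2 speaks only of potential benefits, and exposure and use have their own analyses in SAP 5.3.10.4 and 5.3.10.5. All of this stands, and it keeps the point minor. It does not remove the bias. Nor is total exposure a clean substitute: its rule for a catheter never removed covers participants still in the investigation and does not say what happens at death.

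The size is also assumed. Planned attrition is not split by cause, does not name transplant or PD transfer, and sits beside an inclusion criterion of at least 24 months' expected lifespan. The spread from 2.9 to 21.6 points shows how little the documents determine. This stands too.

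Two stronger readings are tempting. A reader might infer that participants who die are treated as if the catheter had certainly come out. They are not: they receive the later removal chance of those still at risk, which approaches certainty only as the Kaplan-Meier curve approaches full removal. A reader might also infer that censoring at transplant or PD transfer inflates the figure in the same way. The documents do not establish that. The event is any removal, not removal because the fistula is in use. The censoring rule applies only without removal. Neither transplant nor PD transfer is among the discontinuation reasons listed in CIP 6.5, so a removal afterwards can still be observed and may count. The text is unclear on this, and counting all such participants as never freed of the catheter could understate removal.

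**Conclusion.** The point holds for death with the catheter in place. The removal proportion in SAP 5.3.10.1 and 5.3.10.2 is biased upward, in the device's favour, and that direction needs no assumption about rates. It rests on two inferences from the text: that death counts as discontinuation, which the CIP supports, and that the reported proportion is 1-KM, which is the natural reading.

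The size is illustrative only: about 2 to 7 points at 24 months under the first set of assumptions, and more under others. For death alone, the competing probabilities in the tables must be read as deaths. For transplant and PD transfer the finding is an undefined counting rule, not a demonstrated bias. No power, type I error or primary conclusion is affected. This is a cheap improvement to an exploratory analysis.

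**What to change.** In SAP 5.3.10.1 and 5.3.10.2:

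- Report the Aalen-Johansen cumulative incidence of CVC removal, with death with the catheter in place as a competing event, and show the incidence of that competing event beside it.
- Censor at withdrawal, loss to follow-up and the data cut, and name death separately from these.
- State whether a catheter removed after kidney transplant or PD transfer counts as the event. If it does not, treat transplant and PD transfer as separate competing events instead of censoring them.
- Keep the Kaplan-Meier curve, if wanted, as a supportive cause-specific analysis.

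No new data are needed. The removal, transplant and PD dates are already used in this analysis, and CIP 8.5 requires every death to be reported. The cost is SAP wording, minor extra programming and a slightly less favourable figure.

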#### 5.3.10.2 Time to CVC Removal

Same analysis as 5.3.10.1. The analysis will be performed for the entire AT population. For participants that do not have a CVC in place (or placed) at the time of the index procedure, the time to CVC removal of the first placed CVC chain after the index procedure will be included.

## 5.3.10.3 Frequency of CVC Placements

The number of CVC placements will be evaluated at 30-days, 6-weeks, 3-, 6-, 12-, 18-, and 24-months post creation on the AT population. The number of CVC placements will include the CVC already in place at the index procedure. When a participant has a chain of CVC placements (where the Date of Placement of an exchanged CVC is within one day of the Date of Removal of the previous CVC), the analysis will be done in both ways: (1) only the first CVC replacement is counted, and (2) each CVC replacement is counted separately.

## 5.3.10.4 Total Days of CVC Exposure

Total days of CVC exposure will be calculated by (Date of Removal minus Date of Placement +1 summed across all CVCs a participant is exposed to during the follow up). When the CVC placement occurs prior to index procedure, Date of Index Procedure will be used for the calculation. If the participant is still in the investigation without having a CVC removed by the cutoff date of database lock, the cutoff date of database lock will be used for the calculation. When a participant has a chain of CVC placements where the Date of Placement of an exchanged CVC is within one day of the Date of Removal of the previous CVC, it is considered one CVC placement, and the corresponding total days of CVC exposure will be accumulated. This endpoint will be assessed on the AT population.

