## 2.4 Sample Size

The sample size for the investigation of one-hundred and fifty (150) treated participants was established to assure adequate power for the primary safety and effectiveness endpoints as well as to result in a sufficient sample size (when accounting for attrition) for assessment of the secondary and exploratory endpoints, specifically for those that only apply to subsets of the overall population (i.e., the incident population and wrist arterial procedure access population).

- 1) Primary Safety Endpoint The proportion of participants with freedom from device- or procedure-related SAEs through 30 days (ITT Population).
  - Assumptions:
    - The freedom from device- or procedure-related SAE rate for AVFs created using the WavelinQTM EndoAVF System is estimated at 92.6% through 30 days based on pre-market data;
    - The PG is set at 82.6% using a 10% non-inferiority margin;
    - o The rate of attrition through 30 days is assumed to be 10%; and
    - o The Type 1 error is 0.05 (two-sided).
  - Sample Size:
    - o A sample size of 150 treated participants [135 evaluable] will give over 92.5% power with a two-sided type I error of 0.05 as calculated using PASS 2019 (One Proportion Exact Test).
- 2) Primary Effectiveness Endpoint Interventions Post Creation to Facilitate AVF Use and / or Maintain AVF Use (Facilitation and / or Maintenance Interventions) through the Timepoint of the 6-Month Follow-Up of the Last Active Treated Participant (AT Population)
  - Assumptions:
    - The number of interventions post creation to facilitate AVF use and / or maintain AVF use after AVF creation using the WavelinQTM EndoAVF System is estimated at 3.0 / PY, a conservative assumption based on pre-market data;
    - The PG is set at 5 / PY to align with the targets and recommendations of the 2019 update of the KDOQI Clinical Practice Guideline for Vascular Access of ≤ 2 interventions to facilitate and ≤ 3 interventions to maintain AVF use:
    - The rate of attrition through 6-, 12-, and 24-months, including lost to follow-up, death, and other clinical investigation premature withdrawals is assumed to be 20%, 40%, and 60%, respectively; and
    - o The Type 1 error is 0.05 (two-sided).
  - Sample Size:

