Length of investigation duration (Days) is from the date of index procedure to the cutoff date of database lock (cutoff date – date of index procedure +1). If a participant discontinued early, then the last date of available study data (including the unscheduled visit date) will be used to calculate the length of investigation duration (last date of

available study data – date of index procedure +1). If a participant's endoAVF has permanent abandonment the date of permanent abandonment will be used to calculate the length of investigation duration (permanent abandonment date – date of index procedure +1).

The primary effectiveness analysis will be conducted on the AT population after the last active treated participant completes their 6-month follow-up; by this time, all participants still in the clinical investigation will have at least 6-months of data. The number of Facilitation and / or Maintenance Interventions per PY will be estimated by Poisson regression model with only the intercept term, and the estimate and 95% CI will be provided using the Wald method, and the p-value comparing to the PG will be calculated by a Chi-square test. The analysis will be repeated on the PP population.

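### Total CVC days are a raw sum with no follow-up denominator and no stated end date for leavers with a catheter in place, so the figure falls as attrition rises

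*SAP*

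**What the plan says.** SAP 5.3.10.4 defines the summary for the as-treated (AT) population: "Total days of CVC exposure will be calculated by (Date of Removal minus Date of Placement +1 summed across all CVCs" that the participant has during follow-up. Two date rules accompany it.

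- Start: "When the CVC placement occurs prior to index procedure, Date of Index Procedure will be used for the calculation".
- End: "If the participant is still in the investigation without having a CVC removed by the cutoff date of database lock", the cutoff date stands in for the removal date.

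The section says nothing about a participant who has left the study with a CVC in place. It does not divide by follow-up time and names no time point. SAP 2.7.3.13 and protocol 4.3 speak only of total days, so they do not fill the gap.

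Two other parts of the SAP do handle leavers. The Kaplan-Meier analysis of time to CVC removal (5.3.10.1) censors them at the "last date of available study data including the unscheduled visit date". The primary effectiveness endpoint (5.1.2) works per patient-year and states: "If a participant discontinued early, then the last date of available study data (including the unscheduled visit date) will be used" to end the person-time.

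For attrition at 6, 12 and 24 months, SAP 2.4 says the rate "is assumed to be 20%, 40%, and 60%, respectively".

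**The concern.** A sum of days can grow only while a participant is observed. Observation time differs between participants for two reasons: staggered entry at the 6-month reporting, and attrition at both reportings. Without a denominator or a fixed horizon, the mean mixes catheter behaviour with length of follow-up.

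The missing end date adds to this. For a leaver whose CVC was never recorded as removed, the formula has no second date. The programmer must end the catheter at the last data, leave the participant missing, or give that catheter zero days. Each choice yields a different mean, and the section does not choose.

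Protocol 9.2 names less catheter exposure as a possible benefit of the device. A summary that looks better when more people leave is weak support for that statement.

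**Working it through.** **Inputs from the documents.** 150 treated participants; attrition 20/40/60% at 6/12/24 months; more than 100 patient-years (PY) expected at the 6-month reporting (SAP 2.4). Accrual of about 18 months and 24 months of follow-up (protocol 3). The documents give no CVC rates.

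**Step 1: reproduce the plan's person-time.** Assume that retention falls in straight lines through 1, 0.8, 0.6 and 0.4 at 0, 0.5, 1 and 2 years, and that accrual is uniform. Planned follow-up at the 6-month reporting then runs from 0.5 to 2.0 years.

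- Mean observed time = (1/1.5) × [∫₀^0.5 (0.45 + 0.8u − 0.2u²) du + ∫₀^1 (0.8 + 0.6u − 0.1u²) du] = (0.3167 + 1.0667)/1.5 = 0.922 years.
- 150 × 0.922 = 138.3 PY (137.4 with log-linear retention). This agrees with the stated figure of more than 100 PY.
- Without attrition the mean is (0.5 + 2.0)/2 = 1.25 years. The loss is 1 − 0.922/1.25 = 26%.

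**Step 2: final reporting.** Mean observed time = 0.5 × 0.9 + 0.5 × 0.7 + 1.0 × 0.5 = 1.30 years, or 474.5 of 730 days. The loss is 1 − 1.30/2.00 = 35%.

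**Step 3: constant CVC share.** Suppose 30% of follow-up days are CVC days. Mean total without attrition = 0.30 × 730 = 219 days. With the plan's attrition it is 0.30 × 474.5 = 142 days, a fall of 35%. The rate is 300 per 1,000 follow-up days in both cases.

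**Step 4: front-loaded CVC use (illustration).** Assumptions: 60% have a CVC at index; time to removal is exponential with median 3, 6 or 12 months; no later CVC; leaving is independent of the catheter; 24-month horizon; 400,000 simulated participants. Days for a participant with a CVC = 365 × min(removal, exit, 2 years). Mean CVC days per AT participant:

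| Attrition and treatment of a leaver's open CVC | Median 3 months | 6 months | 12 months |
|---|---|---|---|
| No attrition | 78.7 | 148.2 | 236.5 |
| 10/20/30%, ended at last data | 73.3 | 132.0 | 203.3 |
| 20/40/60%, ended at last data | 67.9 (−14%) | 115.7 (−22%) | 170.3 (−28%) |
| 20/40/60%, leaver dropped as missing | 63.2 (−20%) | 104.4 (−30%) | 152.6 (−35%) |
| 20/40/60%, open CVC counted as 0 days | 58.0 (−26%) | 89.2 (−40%) | 119.6 (−49%) |

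Under 20/40/60% attrition, 8.4%, 14.5% and 21.6% of participants leave with a CVC in place. Those are the participants for whom 5.3.10.4 states no end date.

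**Step 5: would a simple rate repair it?** In the same simulation, with open catheters ended at last data, CVC days per 1,000 follow-up days move from 107.7 to 143.2 (+33%), 203.0 to 243.5 (+20%) and 324.0 to 359.1 (+11%) between no attrition and 20/40/60%. Attrition removes mostly late follow-up, when few catheters remain, so the crude rate rises although nothing about the catheters has changed.

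**The case against.** The strongest reply is that little depends on this figure and that much of it is covered elsewhere.

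- **Exploratory status.** Protocol 7.6 allows exploratory endpoints to be left out of the report. The summary is descriptive and single-arm, with no performance goal. This stands and limits the importance of the point.
- **Appendix 2.** SAP 3.2 sends derived-data rules to Appendix 2, of which only the title is available. A reader might infer that the plan has no end date at all for leavers. The documents support only that 5.3.10.4 states none.
- **Kaplan-Meier analyses.** SAP 5.3.10.1 and 5.3.10.2 censor leavers properly. This stands, but they follow only one chain of catheters per participant and do not measure total exposure.
- **Size.** A reader might take 35% as the general size of the effect. It holds only if CVC use is a constant share of follow-up. Protocol 2.1.2 reports a mean time to cannulation of 2.0 months in earlier studies, which suggests front-loaded use and a smaller fall. Attrition also includes deaths, and days after death are not missed exposure, so the whole shortfall should not be called bias.
- **Direction.** Totals would rise with attrition if a leaver's open CVC ran on to 24 months (118.9, 195.2 and 277.4 days in the simulation). The condition that the participant is still in the study excludes this reading.
- **Placement count.** SAP 5.3.10.3 says "The number of CVC placements will include the CVC already in place at the index procedure". A reader might infer that the count mainly reflects how many catheter patients were enrolled, or that leavers' last catheters tend to be the longest. The documents give no baseline CVC share, placement rate or duration, so neither follows. Including the baseline CVC is an openly stated choice. Post-index CVC placement also enters the all-interventions rate per PY (protocol Table 1, SAP 5.3.6), though pooled with other procedures.

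**Conclusion.** The point holds as a minor one. As written, 5.3.10.4 yields a mean that falls as attrition rises with unchanged catheter behaviour, and it leaves the end date open for leavers with a CVC in place, subject to Appendix 2. The fall is 35% at final reporting with a constant CVC share. It is about 14% to 49% in the illustration, depending on removal time and on how the open catheter is read. These sizes rest on the plan's attrition, straight-line retention and, for the range, assumed CVC rates and leaving that is unrelated to the catheter. The direction is the same under all three readings that the text leaves open. No hypothesis test, sample size or primary conclusion is affected.

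**What to change.** Change SAP 5.3.10.4 as follows.

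1. End each CVC at the earliest of its removal date, the participant's last date with data (including death) and the reporting time point. This matches 5.1.2 and 5.3.10.1. It also settles the end date for completers at final reporting, when every participant has completed or discontinued. If Appendix 2 already holds such a rule, cite it here.
2. Lead with mean cumulative CVC days at the time points already used in 5.3.10 (30 days, 6 weeks, 3, 6, 12, 18 and 24 months), using a method that handles censoring. State how death is treated.
3. Give CVC days per follow-up day as a supportive figure, with a note that a crude rate rises with attrition when catheter time is front-loaded.
4. Optionally, in 5.3.10.3, show CVCs already in place at index separately from later placements.

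The cost is revised SAP wording and table shells and slightly more analysis work. No new data are needed.
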